Patients in **Arm A (resectable cohort)** will receive nivolumab at 240 mg IV every 2 weeks for 3 doses followed by liver imaging and hepatic resection on day 1 of week 7, followed (after 4 weeks from surgery) by nivolumab 480 mg IV every 4 weeks in the adjuvant setting until disease progression or for 2 years, whichever is sooner. Patients in **Arm B (resectable cohort)** will receive nivolumab 240 mg IV every 2 weeks for 3 doses plus ipilimumab 1 mg/kg IV on day 1 of therapy (3 doses of nivolumab, 1 dose of ipilimumab) followed by hepatic resection followed (after 4 weeks from surgery) by nivolumab 480 mg IV every 4 weeks plus ipilimumab 1 mg/kg IV every 6 weeks to 4 doses in the adjuvant setting. Adjuvant therapy will start after 4 weeks from surgery with nivolumab 480 mg IV every 4 weeks (Both Arms A and B) plus ipilimumab 1 mg/kg IV every 6 weeks (in Arm B only) for up to 4 doses in the adjuvant setting until disease recurrence or for total of 2 years from first cycle, whichever is sooner. For Arm B, ipilimumab will be administered before nivolumab since the toxicities for ipilimumab are already well-known. Since the doses of nivolumab and ipilimumab either as monotherapy or combination are within maximum tolerated doses as previously defined, no dose increases or reductions will be allowed.

Patients will return at week 6 for a pre-surgical evaluation. A small portion of patients with rapid disease progression (We anticipate 1-3 of a total of 30 patients in Arms A and B) may not have hepatic resection per discretion of the treating surgical and medical oncologists. These patients will be off protocol and treated with other standard or investigational agents. They will be asked to return for an optional biopsy that will be scheduled in place of their surgery. For patients who had significant progression of disease pre-operatively but are still eligible for hepatic resection or transplantation, they will be treated with other investigational agents vs. observation post-operatively as there is no standard adjuvant therapy in surgically resected HCC.

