12.2.2 Secondary Endpoints

12.2.2.1. *Objective Response Rate (ORR)*

Objective response rate (ORR) is defined as the number of subjects with a best response of CR or PR after 12 weeks of therapy by RECIST 1.1 criteria divided by the number of randomized subjects as described in Section 10.3.4.2

12.2.2.2. *Time to progression (TTP)*

TTP is defined as the time from the start of study drug to the first documented tumor progression or recurrence of tumor as determined by the investigator using RECIST 1.1 or iRC criteria. Patients who are alive and free of known progression at the time of analysis will be censored on the date of last tumor assessment.

12.2.2.3 *PFS*

PFS is defined as the time from the start of treatment to date of PD or recurrence or date of death whichever occurs first if patients have a event, or to the last follow-up date if patients are alive without PD.

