12.6 Data Analyses

This is a two arm, open-label pilot study evaluating nivolumab alone or in combination with ipilimumab in the preoperative or prebiopsy setting. Since no effective treatments are available in this setting, a response rate of 15% (within 95% CI) is considered acceptable – i.e., the signal for launching further, larger studies with nivolumab or nivolumab + ipilimumab in this patient population is ≥ 1 response in the current study (each arm). If no response is observed, the treatment with nivolumab alone or in combination with ipilimumab will be considered ineffective. A total of 15 patients will be enrolled in each arm and treated to rule out a response rate of 15% or less with 90% power when at least one response is observed. In other words, with 15 patients treated, the probability of observing at least one response is more than 90% if the response rate is at least 15%. Descriptive statistics including with 90% confidence interval will be computed. Observed response profile, clinical benefit rate at 6 months and TTP along with relevant confidence intervals will be used to guide future development decisions.

Total evaluable patients	Number of responders	Response rate	Lower 90% CI*	Upper 90% CI*
15	0	0%	<1%	18%
15	1	7%	<1%	27%
15	2	13%	2%	36%
15	3	20%	6%	44%
15	4	27%	10%	51%
15	5	33%	14%	58%
15	6	40%	19%	64%
15	7	47%	24%	70%
15	8	53%	30%	76%
15	9	60%	36%	81%
15	10	67%	43%	86%
15	>10**	>67%	>43%	>86%

* Exact confidence interval computed by the method of Clopper and Pearson (Biometrika 26:404-413, 1934)

The Kaplan-Meier method will be used to estimate probability of PFS for each treatment arm.

Our exploratory objectives are to characterize the immune response for both treatment arms and its correlation to treatment response. Immune responses, such as infiltration of CD8+/CD4+ T cells and dendritic cells, and cytokine levels in blood, will be compared between pre-treatment and post-treatment via paired t-test and Wilcoxon signed rank test. The overall treatment response rate will be summarized descriptively by dose with the n, percentage, and 95% CIs. Comparison of the response rates between two treatment arms will be made via Fisher's exact test Association

between the binary overall treatment response and immune responses will be assessed by two-sample t-test and Wilcoxon rank sum test.

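### ORR is defined per randomized patient, but the section 12.6 table and the summary reports count evaluable patients, a term never defined for response

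*Combined protocol and SAP*

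**What the plan says.** The combined protocol and SAP uses more than one base for the response rate.

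- **Section 12.2.2.1 (endpoint definition).** The numerator is patients with a "best response of CR or PR after 12 weeks of therapy by RECIST 1.1 criteria". The count is "divided by the number of randomized subjects".
- **Section 12.6 (table).** The column that gives the denominator is headed "Total evaluable patients", and every row has n = 15.
- **Section 12.6 (text).** The plan is that "A total of 15 patients will be enrolled in each arm and treated", and that "with 15 patients treated, the probability of observing at least one response is more than 90" per cent if the true rate is 15% or higher.
- **Section 12.6 (closing paragraphs).** Safety/efficacy summary reports fall due after every 5 evaluable patients per arm, with toxicity read at week 6 and response at week 14.
- **Section 12.5.** Anyone given at least one dose is evaluable for toxicity. No section says who is evaluable for response.
- **Section 5.3.** About 1-3 of the 30 patients in the two arms are expected to progress rapidly and may not be resected. "These patients will be off protocol and treated with other standard or investigational agents".
- **Sections 2.0, 5.3 and 12.1.** Enrolment stopped with 30 enrolled and 27 randomized. The split between arms is not given.

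**The concern.** At the design stage the denominators coincided: 15 enrolled, treated and evaluable per arm. They need not coincide now. The patients most easily called not evaluable for response are those who leave the protocol around week 6 or 7, before the 12-week point in the ORR definition and the week-14 point in the summary reports. These patients are mostly non-responders, so leaving them out would push the ORR upward. If the omissions fall unevenly between arms, they would also distort the Fisher comparison.

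Section 12.6 says that the response profile and its intervals will guide further development. The trial is open-label, so a response-evaluable set that is not defined beforehand could be settled with outcomes in view.

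**Working it through.** **Inputs.** Planned n per arm 15, reference response rate 15%, exact (Clopper-Pearson) 90% intervals and a go signal of at least 1 response per arm (all section 12.6); 1-3 rapid progressors among 30 (section 5.3); 27 randomized (section 12.1).

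**Step 1: reproduce the plan's own figures.** P(at least 1 response) = 1 − (1 − p)^n. With p = 0.15 and n = 15, this is 1 − 0.85^15 = 0.913, which agrees with the plan's statement of more than 90%. The interval limits in the table also reproduce at n = 15, apart from two that differ by about one point: the upper limit for 1/15 is 27.9% (27% printed) and the lower limit for 10/15 is 42.3% (43% printed).

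**Step 2: effect of dropping non-responders.** Assume 15 randomized in an arm and d non-responders left out as not evaluable. The ORR changes from x/15 to x/(15 − d), a factor of 15/(15 − d): 1.07, 1.15 and 1.25 for d = 1, 2 and 3. Exact 90% intervals are in brackets.

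| Dropped | n | 2 responders | 3 responders |
|---|---|---|---|
| 0 | 15 | 13.3% (2.4-36.3) | 20.0% (5.7-44.0) |
| 1 | 14 | 14.3% (2.6-38.5) | 21.4% (6.1-46.6) |
| 2 | 13 | 15.4% (2.8-41.0) | 23.1% (6.6-49.5) |
| 3 | 12 | 16.7% (3.0-43.8) | 25.0% (7.2-52.7) |

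With 2 responders, the point estimate crosses 15% once two patients are dropped.

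**Step 3: comparison between arms.** Suppose both arms have 3/15 and three non-responders are dropped from one arm only. A true observed difference of zero becomes 25.0% − 20.0% = 5.0 points.

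**Step 4: go signal.** The signal is x ≥ 1. Dropping non-responders changes n and leaves x alone, so the signal is unaffected.

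**Step 5: actual arm sizes.** Two arms of 15 need 30 randomized patients, and there are 27. Two arms of 14 would need 28, so the smaller arm has at most 13. At p = 0.15:

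- n = 14: 1 − 0.85^14 = 0.897
- n = 13: 1 − 0.85^13 = 0.879
- n = 12: 1 − 0.85^12 = 0.858

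The statement of more than 90% therefore fails in at least one arm, whatever the split.

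**The case against.** The case for leaving the text alone has several parts.

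- **The denominator is already fixed.** Section 12.2.2.1 names randomized subjects, so anyone without a CR or PR already counts as a non-responder. The section 12.6 table can be read as a planning display at the intended n, and it contains no rule that removes anyone. This stands in part: the fix mostly carries 12.2.2.1 into 12.6. But 12.6 is the analysis section, and neither its table nor the summary reports refer back to that definition.
- **Exclusion is not documented.** A reader might infer that rapid progressors will be left out. The documents do not say so. Imaging is scheduled at week 6 (sections 5.3 and 10.1.3), PD is a listed overall response (Table 4), and best response runs from the start of treatment until progression (section 10.3.4.2). Such patients would normally be recorded as PD. What stands against the plan is that response-evaluability is undefined.
- **A treated denominator is different.** A reader might think that it also loses early progressors. They have been dosed by the week-6 evaluation, so they stay in. Only patients randomized but never dosed would drop out.
- **The go decision is safe.** A reader might infer that the trigger for larger studies is inflated. It is a count (Step 4), so it is not.
- **The shift is small.** The expected 1-3 of 30 is 0.5-1.5 per arm of 15. One patient dropped moves 3 responders from 20.0% to 21.4%, against a 90% interval for 3/15 that spans 44.0 − 5.7 = 38.3 points. A reader might prefer a starker case such as 3/13 = 23.1% rising to 3/10 = 30.0%. That case assumes an arm size the documents do not give and puts the maximum number of progressors, all excluded, in one arm.

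**Conclusion.** The inconsistency is real and worth correcting, with modest consequences. The ORR definition uses randomized patients, while the section 12.6 table and the summary reports use an evaluable set that is undefined for response. That leaves room for an upward bias in the ORR and its interval, and for a distorted Fisher comparison.

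The illustrated size is 1.4 to 5.0 percentage points for 3 responders and 1.0 to 3.4 for 2 responders (14.3 − 13.3 and 16.7 − 13.3). This rests on an assumed arm of 15 with 1-3 non-responders dropped from that arm; three in one arm is the upper end of what section 5.3 anticipates. Crossing 15% with 2 responders could alter how the result is read, but no rule in the plan depends on the point estimate exceeding 15%.

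The documents do not show that anyone will be excluded, and the go signal is not affected. Separately, and without any such assumption, the n = 15 table and the statement of more than 90% cannot hold for both arms with 27 randomized.

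**What to change.** In section 12.6:

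1. Use all randomized patients, by arm, for the ORR, its exact interval and Fisher's test, with a reference to section 12.2.2.1.
2. State that randomized patients with no post-baseline tumour assessment, or off protocol before one, count as non-responders.
3. Compute the intervals at the actual number randomized in each arm, and restate the probability of at least one response at those numbers. Relabelling the n = 15 table would not be enough.
4. If a response-evaluable ORR is wanted, define the set in advance and report it only as a sensitivity analysis. Use the same definition in the summary reports.

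The cost is SAP wording and a recalculated table, with no new data or procedures. The downside is that the ORR may be slightly less favourable than on an evaluable set.

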2.0 OBJECTIVES

Primary Objective:

1. To evaluate the safety and tolerability of therapy with nivolumab alone or nivolumab + ipilimumab in resectable HCC in the context of presurgical therapy.

Note: As of January 8, 2020, 30 patients have been enrolled and 27 patients have been randomized. The PI decided to stop enrollment since the study has reached its primary endpoint of safety.

Secondary Objectives:

1. To assess the efficacy of presurgical nivolumab alone or nivolumab + ipilimumab therapy in HCC by estimating the objective response rate (ORR) and time to progression (TTP) per RECIST 1.1 progression-free survival (PFS).

Exploratory Objectives:

1. To assess the *immunological/biomarker changes* in tumor tissues and peripheral blood in response to nivolumab alone or nivolumab + ipilimumab in HCC therapy (pre- vs post-treatment), and explore any potential association between these biomarker measures and antitumor response and immune-related response criteria (iRC) assessed by MD Anderson Department of Diagnostic Imaging.

[figure not shown]

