3.4.5 Study Rationale

As mentioned, surgical resection or liver transplantation are the only potentially curative treatment modalities for localized HCC in select patients. Local-regional therapies (ie: ablation, arterial-based therapies, or EBRT) can palliate and sometimes downstage non-resectable lesions, but are not typically curative procedures. Sorafenib is the only FDA-approved systemic therapy for advanced HCC. Therefore, patients with unresectable HCC have poor survival and there is a high recurrence rate (~50% or more) for those receiving potentially curative therapy. Novel treatment approaches taking advantage of the higher response rates seen in early-phase HCC studies and long-term survival of immunotherapies clearly need to be studied in order to improve the treatment of HCC. As a basis for future research in HCC, immunological pathways in response to monotherapy versus combinational therapy need to be evaluated in the context of clinical outcome in order to identify predictive and prognostic biomarkers as well as other potential therapeutic targets.

Anti-PD-1 antibody, nivolumab, has recently been shown in a phase 1-2 clinical trial on 42 patients with advanced or unresectable HCC to result in 19% ORR; many of these responses were durable with a response duration of 1-8+ months in patients achieving a PR [34]. Subsequent analysis of 214 patients on this study confirmed a 16% ORR. Of note, these response rates compare favorably to those seen for sorafenib where the ORR = 2% (without any observable CRs). Anti-CTLA-4 antibody, ipilimumab, has not been tested in HCC. However, an alternative anti-CTLA-4 blocking agent, tremelimumab, has been reported to have a partial response rate of 17% in patients with HCC and chronic HCV [42].

Based on strong preclinical data supporting the hypothesis that PD-1 and CTLA-4 are both non-redundant pathways that negatively regulate effector T cells, multiple recent clinical studies in other cancer types suggest that combination nivolumab and ipilimumab may induce even greater anti-tumor responses than either agent alone. While this combination has yet to be tested in HCC, considering the immunosuppressive environment especially characteristic of hepatitis-related HCC, combination therapy may lead to enhanced responses.

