5.3 Study Design and Duration

This is a pilot, randomized, open-label study of preoperative nivolumab alone (Arm A) or nivolumab plus ipilimumab (Arm B) in patients with resectable HCC. **A total of 30 patients will be enrolled as follows: Arm A (15 patients) and Arm B (15 patients).** Patients will be randomized into either Arm A or B.

Note: As of January 8, 2020, 30 patients have been enrolled and 27 patients have been randomized. The PI decided to stop enrollment since the study has reached its primary endpoint of safety.

During screening, patients will be evaluated by a surgeon to determine if they are good candidates for conservative hepatic resection or liver resection with curative intent. All patients will also be required to provide a pre-treatment biopsy with documented tumor involvement by pathologist review.

Originally, this study included a third arm (Arm C) in which 15 unresectable patients were to receive nivolumab 240 mg IV every 2 weeks for 3 doses plus ipilimumab 1 mg/kg IV on day 1 of therapy (3 doses of nivolumab, 1 dose of ipilimumab; 6 weeks) followed by post-treatment biopsy. The study objective in Arm C was to estimate the conversion rate to surgery for potentially resectable patients. However, the study has been amended in June 2019 to remove exclude this objective and enrollment of Arm C (Appendix II).

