12.0 STATISTICAL METHODOLOGY

12.1 Preliminaries and Objectives

This is a randomized, pilot trial of nivolumab (Arm A) or nivolumab + ipilimumab (Arm B) as pre-operative treatment for patients with hepatocellular carcinoma who are eligible for surgical resection. Each patient in both Arms A and B will be given nivolumab at 240 mg every 2 weeks

for a total of 6 weeks. Patients in Arm B will additionally be treated concurrently with ipilimumab at 1mg/kg every 6 weeks. No dose increases or reductions will be allowed for nivolumab or ipilimumab. Surgical resection or post-treatment biopsy will occur within 4 weeks after finishing the last cycle of therapy. The rationale is that nivolumab and ipilimumab activate the immune system via distinct mechanisms and therefore, the combination of nivolumab and ipilimumab may result in synergistic activation of the immune system against hepatocellular carcinoma. The primary objective is to assess the safety and tolerability of nivolumab +/- ipilimumab. Secondary objectives include estimating the ORR and TTP of the 2 different arms. Exploratory objectives include evaluating the pre- and post-treatment immunological changes in tumor tissues and peripheral blood.

As of January 8, 2020, 30 patients have been enrolled and 27 patients have been randomized. The PI decided to stop enrollment since the study has reached its primary endpoint of safety.

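### Section 12.6 plans no between-arm comparison of immune measures, although the rationale raises monotherapy versus combination and patients are randomized 1:1

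*Combined protocol and SAP*

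**What the plan says.** Section 12.6 states the immune aim: "Our exploratory objectives are to characterize the immune response for both treatment arms and its correlation to treatment response". It then names two immune analyses.

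- Immune measures, including T-cell and dendritic-cell infiltration and blood cytokines, "will be compared between pre-treatment and post-treatment via paired t-test and Wilcoxon signed rank test". The text does not say whether this is done by arm or pooled.
- Association "between the binary overall treatment response and immune responses will be assessed by two-sample t-test and Wilcoxon rank sum test".

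The one test between arms concerns clinical response: "Comparison of the response rates between two treatment arms will be made via Fisher's exact test".

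The exploratory objective in section 2.0 covers changes "in response to nivolumab alone or nivolumab + ipilimumab in HCC therapy (pre- vs post-treatment" and their association with antitumor response. The rationale goes further. Section 3.4.5 says "immunological pathways in response to monotherapy versus combinational therapy need to be evaluated" and gives possible synergistic or additive activity as a reason for the trial. Section 12.1 says that "the combination of nivolumab and ipilimumab may result in synergistic activation of the immune system against hepatocellular carcinoma". Section 12.4 randomizes 1:1.

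On specimens, section 5.3 has all patients "required to provide a pre-treatment biopsy with documented tumor involvement by pathologist review". Sections 10.1.4, 10.3.2.3 and 12.2.3 take post-treatment tissue at resection, or by biopsy. Footnote j of both schedule tables in section 10.0 calls for biopsies at both time points, so the post-treatment specimen type is not clear.

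**The concern.** A paired test asks whether a marker moved. It cannot say whether the marker moved more with ipilimumab added, and that is the question that makes a second randomized arm informative about immune activation. With no arm contrast planned, a reader is left to set two within-arm p-values side by side. In small arms, one being significant and the other not is weak evidence of a difference.

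A pre/post change also has no concurrent control. In tumor tissue, a core biopsy before treatment and a piece of a resection specimen after it may differ for reasons unrelated to drug. The paired test counts any such shift as a change. A contrast between randomized arms removes whatever part of the shift is common to both.

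**Working it through.** **The plan's own figure.** Section 12.6 gives one power statement, for response: with 15 patients and a true rate of 15%, the chance of at least one response exceeds 90%. Check: 1 − 0.85^15 = 0.913, which agrees. No figure is given for the immune analysis.

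**Which comparisons are specified (12.6).**

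| Quantity | Pre vs post | Against response | Arm A vs Arm B |
|---|---|---|---|
| Immune measures | yes | yes | no |
| Response rate | – | – | yes (Fisher) |

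No other section fills the empty cell.

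**Inputs for the calculations.** From the documents: 27 patients randomized, 1:1. Assumed, because the documents give no figures: a 14/13 split, complete pairs, SD of the paired change = 1, two-sided alpha 0.05, and the effect and shift sizes below.

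**Side-by-side p-values.** Suppose both arms truly change by 0.5 SD. Noncentral-t power of the paired test is 0.382 with 13 pairs and 0.410 with 14. The chance that exactly one arm is significant is 0.382 × (1 − 0.410) + 0.410 × (1 − 0.382) = 0.225 + 0.253 = 0.48, although the arms do not differ.

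**Specimen shift in tissue, no drug effect, same shift in both arms** (20,000 simulated trials):

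| Shift (SD) | Paired test significant, n = 14 | n = 13 | Between-arm test significant |
|---|---|---|---|
| 0 | 5% | 5% | 5% |
| 0.25 | 14% | 14% | 5% |
| 0.5 | 41% | 38% | 5% |
| 0.75 | 74% | 70% | 5% |
| 1.0 | 93% | 91% | 5% |

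If the paired test is instead pooled over 27 pairs, its noncentral-t rejection rate is 24%, 71% and 96% at shifts of 0.25, 0.5 and 0.75 SD. The last column of the table holds only because the simulated shift is equal in both arms.

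**What an arm contrast can deliver.** The 95% CI half-width for the difference in change is t(0.975, 25 df) × √(1/14 + 1/13) = 2.06 × 0.385 = 0.79 SD. Power is 24% for a difference of 0.5 SD, about 52% for 0.8 SD and 70% for 1.0 SD; 80% power needs 1.12 SD.

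**Gain from baseline adjustment.** With pre/post correlation r and equal variances, the ratio of ANCOVA variance to change-score variance is (1 − r²) / [2(1 − r)] = (1 + r)/2, which is 0.65, 0.75 and 0.85 at r = 0.3, 0.5 and 0.7. The half-width becomes 0.79 × √0.65 = 0.64 SD, 0.79 × √0.75 = 0.69 SD and 0.79 × √0.85 = 0.73 SD, ignoring the one degree of freedom spent on the covariate.

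**The case against.** The strongest defence is that the analysis matches the listed objective. Section 2.0 asks for pre/post change and its association with response, and 12.6 tests both. The sentence in 3.4.5 is framed as a basis for future research and points to biomarkers, which the response-association test partly serves. Section 12.1 offers synergy as the reason for the combination, not as a quantity to estimate. Section 12.3 sizes the trial for toxicity and preliminary estimates. All of this stands. It limits the point to a mismatch between rationale and exploratory analysis; it does not supply the missing comparison.

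Section 10.3.3 refers sample collection and analysis to a separate laboratory protocol that is not available here. Specimen handling may be settled there, so the specimen issue is a possibility to close off, not a demonstrated bias.

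The arm contrast also has low power. That is a reason to report it as an interval, not a reason to leave it out of a pilot meant to inform later trials.

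Several stronger readings are tempting but unsupported:

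- That immune measures are tested only before versus after. They are also tested against response.
- That the arms are never compared. Response rates are, by Fisher's exact test.
- That the plan will read significance in one arm alone as synergy. No section says so; the 48% figure measures the risk if someone does.
- That the specimen issue undermines all immune results. It cannot affect blood markers.
- That an arm contrast always removes the specimen effect. It does so only if specimen types are balanced. Section 5.3 expects 1 to 3 of 30 patients to miss resection, with an optional biopsy instead, and that loss is related to outcome.
- That complete paired tissue is assured. Section 10.3.2.3 speaks of available tissue.

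**Conclusion.** The point holds in limited form. Section 12.6 specifies no between-arm comparison of immune measures, while the rationale raises monotherapy versus combination and the 1:1 randomization would support one. Tissue pre/post changes are additionally open to specimen differences that the documents neither rule out nor address.

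If the arms changed equally by 0.5 SD, within-arm tests would disagree in about 48% of trials. A between-arm estimate would carry a 95% half-width of about 0.79 SD on change scores, or 0.64 to 0.73 SD after baseline adjustment. These figures rest on the assumed 14/13 split, complete pairs and SD of change of 1; the shift sizes are illustrations, not estimates from the documents. Missing pairs would widen the intervals and could weaken the protection of randomization.

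The matter concerns an exploratory endpoint in a safety pilot. The primary safety endpoint and the secondary efficacy endpoints are unaffected. It is worth correcting because the change is cheap and uses information the design already provides.

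**What to change.** In section 12.6:

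1. Add an exploratory Arm B minus Arm A contrast of the post-treatment immune value, adjusted for the pre-treatment value, on a log or rank scale for skewed markers. Report it with a CI, as estimation and not as a powered test.
2. For blood, use the presurgical draws at C2, C3 and C4, which footnote h schedules identically in both arms, in one baseline-adjusted repeated-measures model.
3. For tissue, state the specimen type at each time point, reconcile footnote j with sections 10.1.4 and 10.3.2.3, and report specimen type and number of missing pairs by arm.
4. Say whether the pre/post tests are by arm or pooled, keep them as description, and state that no arm difference will be inferred from within-arm p-values.

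The cost is SAP wording and a little more analysis, with no additional sampling. The price in interpretation is wide intervals, which should be said openly.
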